---

**LIST OF ABBREVIATIONS AND RELEVANT DEFINITIONS**

|         |  |
|---------|--|
| AE      | Adverse Event  |
| AIMDD   | Active Implantable Medical Devices Directive                               |
| BPI     | Brief Pain Inventory   |
| BSI     | British Standard Institution   |
| CE mark | Conformité Européenne (In accordance to European Regulations)              |
| CIBG    | executive agency of the Dutch Ministry of Health, Welfare and Sport        |
| CRF     | Clinical Research Form   |
| CRPS    | Complex Regional Pain Syndrome   |
| CV      | Curriculum Vitae   |
| DSMB    | Data Safety Monitoring Board   |
| DRG     | Dorsal Root Ganglion   |
| EQ-5D   | © 1987 EuroQol Group. EQ-5D™ is a trade mark of the EuroQol Group          |
| EU      | European Union   |
| FBSS    | Failed Back Surgery Syndrome   |
| FU      | Follow Up  |
| GCP     | Good Clinical Practice   |
| INS     | Implantable NeuroStimulator  |
| IRAS    | Integrated Research Application System                                     |
| ISO     | International Organisation for standardisation                             |
| OLBPDQ  | Oswestry Low Back Pain Disability Questionairy                             |
| REC     | Research Ethical Committee   |
| SAE     | Serious Adverse Event  |
| SAS     | Statistical Analysis System  |
| SCS     | Spinal Cord Stimulation  |
| Sponsor | The party that commissions the organisation or performance of the research |
| SPSS    | Statistical computer program   |
| TNS     | Trial NeuroStimulator  |
| VAS     | Visual Analogue Scale  |

## SUMMARY

**Rationale:** Initial clinical studies have shown that stimulation of the dorsal root ganglion (DRG) can significantly reduce chronic intractable pain. These results have supported the CE marking of the Spinal Modulation Neurostimulator system in the management of chronic pain. As DRG stimulation with the Axium® Neurostimulator System is a new type of Spinal Cord Stimulation (SCS) and to follow the requirements of the AIMDD, Spinal Modulation would like to collect clinical data on this commercially available therapy.

**Objective:** The purpose of this PRospEctive post market trial of Drg stlimulation ("PREDICT") is to evaluate the commercially available Axium® Neurostimulator System in the management of intractable chronic pain in patients that are routinely scheduled to receive a Spinal Modulation Axium® Neurostimulator System.

- Primary Objective: Evaluate reduction in pain (VAS)
- Secondary Objectives: Safety (AE/SAE), Quality of life, Physical functioning, Subject satisfaction and Device performance

**Study design:** This is a prospective, post market, multi centre, single-arm trial.

**Device:** Commercially available, CE marked, Axium® Neurostimulator System for the management of chronic intractable pain (CE 567069).

**Study population:** Up to 125 Males and females at least 18 years of age suffering from chronic neuropathic pain for at least 6 months that are routinely scheduled to receive a commercially available Axium® Neurostimulator System.

**Intervention:** Under monitored anaesthesia care, subjects will undergo minimally invasive placement of leads in the lateral epidural space of the neural foramen following standard clinical procedures. Subjects having successful trial stimulation will receive the fully-implantable system and will be followed for 24 months. They will be asked to complete several questionnaires at baseline and at follow-up visits.

**Follow-up visits:** The patients will visit the hospital for the following visits: Baseline, Trial NeuroStimulator (TNS) procedure, End of TNS (if applicable), Implantable NeuroStimulator (INS) procedure, 1 week follow-up (FU), 4 week FU, 3 month FU, 6 month FU, 12 month FU and 24 month FU. If needed the site can contact the patients by phone at 8 weeks FU, 9 months FU, and 18 months FU.

**Risks:** There are no additional risks for the patients by participating in this prospective post market trial. The implantation of the system is a standard clinical procedure in the hospital and the additional data that will be collected consists only of questionnaires.

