## 2. OBJECTIVES

The objective for this prospective, multi centre DRG stimulation trial is to assess the performance of the commercially available CE marked Axium® Neurostimulator System in the management of chronic intractable pain.

Primary objectives:

1. Pain relief measured using a Visual Analogue Scale (VAS). The average pain reduction experienced as well as the percentage of subjects with at least a 50% pain reduction will be evaluated.

Secondary Objectives:

[figure not shown]

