**4. STUDY POPULATION****4.1 Population**

████████ male and female subjects (minimum age 18 years old) suffering from chronic intractable pain for a minimum of 6 months who are routinely scheduled for DRG stimulation will be recruited █████ for inclusion in the trial.

Subjects must meet all of the inclusion and none of the exclusion criteria to be enrolled in the prospective trial. Subjects will read and sign an informed consent prior to undergoing any data collection or trial treatment. Subjects will be recruited from the sites existing patient population and through new patient contacts as normally progresses in standard clinical practice.

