**4.2 Inclusion criteria**

- 1) Subject is at least 18 years old
- 2) Subject is able and willing to comply with the follow-up schedule and protocol
- 3) Chronic, intractable pain for at least 6 months
- 4) Failed conservative treatments for chronic pain including but not limited to pharmacological therapy, physical therapy and interventional pain procedures for chronic pain
- 5) Average baseline pain rating of 60 mm on the VAS in the primary region of pain
- 6) In the opinion of the Investigator, the subject is psychologically appropriate for the implantation for an active implantable medical device
- 7) Subject is able to provide written informed consent

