## 6. DESCRIPTION OF THE DEVICE

### 6.1 Name and description of Axium® Neurostimulator System

On 16 November 2011, BSI granted Spinal Modulation, Inc. CE mark for the Axium® Neurostimulator System for the Management of Chronic Intractable Pain (CE 567069). The system has been registered with the CIBG in the Netherlands on 24 November 2011.

The Spinal Modulation Axium® Neurostimulator System consists of the following components:

- Trial NeuroStimulator (TNS)
- Implantable NeuroStimulator (INS)
- Trial Lead Kit
- Implant Lead Kit
- Connector Cable Kit
- Tunnelling Tool Kit
- Clinical Programmer
- Patient Programmer
- Auxiliary Magnet Kit
- Programmer Charger Kit
- Programmer Carrying case
- Lead Accessories Kit
- 22 cm Small Curve Delivery Sheath Kit
- 22 cm Big Curve Delivery Sheath Kit
- Lead Extension Kit

A detailed description of the components can be found in the physician implant manual.

Briefly, the Axium® Neurostimulator System is a fully implantable medical device designed to aid in the management of intractable chronic pain. The device, which is surgically placed in a similar fashion to other approved spinal cord stimulator systems, produces controlled electrical stimulation to spinal neural tissue. A minimally invasive procedure, similar to that used by other approved spinal cord stimulator systems is used to place the device in the body. Also similar to approved spinal cord stimulator systems, individuals first undergo a trial phase in which they can test the effects of the stimulation. If they wish to continue with the therapy they will receive a fully implantable system. The implantable system is reversible in that it can be explanted at any time.

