### 7.3 Study procedures

1.15 Study procedures  
During the prospective trial, data will be collected on Case Report Forms (CRFs). A copy of the CRFs will be provided for review.

*Subject Screening and baseline*

Subjects presenting with chronic pain for at least 6 months will be screened for possible entry into the prospective trial. Subjects will be screened according to the Inclusion/Exclusion criteria and only subjects meeting all Inclusion criteria and none of the Exclusion criteria will be enrolled. The prospective trial will be explained to all subjects and subjects will provide informed consent with an REC-approved Informed Consent Form prior to any data collection. Subjects will be allowed to discuss their participation in the trial with the study physician, clinical staff, family, friends and personal or external physician.

Following subject screening and acquisition of Informed Consent, subjects will undergo a baseline assessment to collect clinical data prior to lead implantation and stimulation. Baseline pain scores (VAS) will be evaluated using the average score from a 4 day pain diary completed by subjects before their trial procedure. Women of child bearing potential will take an HCG-based pregnancy test to confirm that they are not pregnant prior to entry into the trial.

*Trial Stimulation Lead Implant Procedure*

Following collection of baseline measurements, subjects will begin Phase 1 of the two-step treatment process. Phase 1 is the Trial Phase and consists of percutaneously implanting quadrapolar neurostimulator leads into the epidural space. The techniques used in implanting the Spinal Modulation Neurostimulator System are consistent with standard of care practices used by other approved spinal cord stimulator systems. The *Physician Implant Manual* provides a detailed description of the implant and surgical technique. Perioperative programming will be performed to verify proper lead placement.

*End of Trial Phase*

At the end of the Trial Phase, pain relief will be assessed to determine whether a subject should receive an INS implant. This may be done in the theatre during the TNS procedure or after an extended trial period of no more than 30 days based upon the type of pain, the location of the pain, and the standard procedures at the hospital.

*INS Implant Procedure*

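### Does the Summary's reference to neuropathic pain define a different study population from Sections 4.1 and 4.2?

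*Protocol*

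**What the plan says.** The Summary gives the study population as "Up to 125 Males and females at least 18 years of age suffering from chronic neuropathic pain for at least 6 months", limited to patients already scheduled for the device. The Objective in the same Summary is to evaluate the system "in the management of intractable chronic pain in patients that are routinely scheduled to receive" it, with no mention of a neuropathic origin.

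The body of the protocol uses the second description. Section 4.1 recruits subjects "suffering from chronic intractable pain for a minimum of 6 months who are routinely scheduled for DRG stimulation". Inclusion criterion 3 in Section 4.2 reads "Chronic, intractable pain for at least 6 months". Section 2 sets the objective as "to assess the performance of the commercially available CE marked Axium® Neurostimulator System in the management of chronic intractable pain".

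Enrolment is tied to the criteria in two places. Section 4.1 states: "Subjects must meet all of the inclusion and none of the exclusion criteria to be enrolled in the prospective trial". Section 7.3 repeats that "only subjects meeting all Inclusion criteria and none of the Exclusion criteria will be enrolled".

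**The concern.** Neuropathic describes where pain comes from. Intractable describes how it has responded to treatment. The two words are not interchangeable, and a patient with intractable pain of non-neuropathic origin would meet criterion 3 while falling outside the Summary's description.

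The Summary line does not read like loose shorthand. It gives the same minimum age, pain duration and scheduling condition as Section 4.1, and then adds a restriction that the body never states.

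The label matters because the trial has no comparator. Its primary objective is the average reduction in VAS pain and the percentage of subjects with at least a 50% reduction, and a reader interprets both through the description of who was treated. Someone who took that description from the Summary alone could present the results as evidence in neuropathic pain, which no eligibility criterion establishes.

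**Working it through.** No arithmetic applies. The figure of up to 125 subjects is not in dispute, and the sample size text in Section 4.4 is not visible in the public copy. The check is a comparison of the statements, sorted by what each one does.

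| Place in the protocol | Pain described as | What the statement does |
|---|---|---|
| Summary, Study population | chronic neuropathic | summarises who is studied |
| Summary, Objective | intractable chronic | states the aim |
| Section 2 | chronic intractable | states the aim |
| Section 4.1 | chronic intractable | defines who is recruited |
| Section 4.2, criterion 3 | chronic, intractable | decides who is enrolled |
| Section 6.1 | chronic intractable | gives the CE-marked indication ("for the Management of Chronic Intractable Pain (CE 567069") |
| Section 7.3 | chronic | says who is screened |

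1. **Is the difference real?** Yes. Outside two titles in the reference list, the word neuropathic appears only in the Summary line. The blacked-out parts of Section 4.1 lie before and after the pain definition, which is fully legible.

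2. **What kind of difference is it?** The line adds an origin and drops intractability. It is narrower on the first attribute and wider on the second, so the two populations are not nested. The line differs from Section 4.1 and is not simply a stricter version of it.

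3. **How many statements conflict directly?** Fewer than a count of phrases suggests. A study population may properly be narrower than a device's indication or a general aim, so the Objective, Section 2 and Section 6.1 do not by themselves contradict the Summary line. The statements that define entry are Section 4.1 and criterion 3, with the screening text in Section 7.3 in support.

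4. **Does the line act on anything?** The criteria number 7 + 11 = 18, and 0 of the 18 name neuropathic pain. Sections 4.1 and 7.3 make those criteria the test for enrolment. An investigator therefore has one rule to apply, and the Summary line is not part of it. The intractability that the line omits is still required by criterion 3 and supported by criterion 4, which asks for failed conservative treatment.

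5. **Does any figure depend on it?** None that is shown. Neither primary measure in Section 2 is defined by pain origin.

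**The case for a change.** The strongest case for acting is that the target population is core protocol content, that two statements of it disagree, and that aligning one line would cost almost nothing. Section 11.5 also provides for public registration and publication, so the wrong label could travel.

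The first part stands: the statements do disagree, and a synopsis should not add a restriction that the body lacks. The predicted harm is weaker. It needs a reader who relies on one line and passes over the Objective in the same Summary, Section 2, Section 4.1 and the criteria. Nothing shown says that results will be reported under the Summary's label.

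A second point cuts deeper. The protocol does not say which wording was meant. Had the sponsor intended a neuropathic population, the criteria would be at fault, and the remedy would reach well beyond one line. That cannot be excluded from the text alone. But Section 4.1, criterion 3, the stated aims and the device indication all agree with one another, and nothing in the screening procedure or the criteria assesses pain origin. A slip in the Summary is much the more plausible reading.

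**Conclusion.** The inconsistency exists, but it calls for no change to the plan. One adjective in a synopsis departs from the operative sections, and those sections settle who enters the trial. The shown effect on enrolment, on any stated figure and on either primary measure is nil. Rewording the line would tidy the document without altering what is done or what is estimated.

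This rests on two assumptions. The first is that sites enrol by the inclusion and exclusion lists, as Sections 4.1 and 7.3 require. The second is that the body of the protocol reflects the sponsor's intention, which its wording strongly suggests but does not state. On those terms an analyst would describe the subjects by the criteria under which they were enrolled, and the mismatch does no damage.

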## 1. INTRODUCTION AND RATIONALE

### 1.1 History

Neuromodulation for the treatment of chronic pain has been used for over a century. The first use of electricity in the spine for neuromodulation of pain was conducted by Norm Shealy in 1967. The development of spinal cord stimulation (SCS) technology has grown rapidly in the past 40 years and is now used in over 40,000 new patients each year.

### 1.2 Spinal Neuromodulation

Several recent systematic reviews have provided evidence that this stimulation technology is a safe and, to a lesser extent, effective treatment option for patients suffering from chronic, intractable pain. The effective rate of serious complications is quite low. The treatment has been found to be successful in approximately 50% of patients that have a successful temporary stimulation trial period. In the largest prospective trial published to date, Kumar and colleagues found a significant reduction in leg pain when compared to a conventional medical management control group. In a similar manner, Kemler and colleagues found that Spinal Cord Stimulation (SCS) can be effective in the treatment of complex regional pain syndrome (CRPS). Despite varying levels of success in the literature, approximately 50% of patients will not receive adequate pain relief from traditional spinal cord stimulation. This suggests that alternative neuromodulation techniques are needed to improve pain relief in these patients.

### 1.3 Therapy Description

The Axium® Neurostimulator System consists of a two-phase treatment process: 1) a temporary trial phase and 2) a permanent implant phase. The first phase involves implanting stimulation electrodes (or “leads”) into the epidural space, which are connected to an external Trial NeuroStimulator (TNS) to electrically stimulate the Dorsal Root Ganglion (DRG). If the patient experiences sufficient pain relief during this trial stimulation they will progress to receive a fully Implantable NeuroStimulator (INS) system.

### 1.4 Rational

Given the success in treating various pain conditions with electrical neuromodulation techniques and the role the Dorsal Root Ganglion (DRG) plays in the development and maintenance of chronic pain, we have developed a neurostimulator system designed for the management of chronic intractable pain by electrically stimulating the DRG.

As DRG stimulation with the Axium® Neurostimulator System is a new type of Spinal Cord Stimulation (SCS) and to follow the requirements of the AIMDD, Spinal Modulation would like to collect clinical data on this commercially available therapy. This multi-centre trial is set up to collect long term prospective data on the performance of the Axium® Neurostimulator system in patients that are routinely scheduled to receive DRG stimulation in the management of chronic intractable pain.

## 2. OBJECTIVES

The objective for this prospective, multi centre DRG stimulation trial is to assess the performance of the commercially available CE marked Axium® Neurostimulator System in the management of chronic intractable pain.

Primary objectives:

1. Pain relief measured using a Visual Analogue Scale (VAS). The average pain reduction experienced as well as the percentage of subjects with at least a 50% pain reduction will be evaluated.

Secondary Objectives:

[figure not shown]

## 3. STUDY DESIGN

This study is a prospective, post market, single-arm, multi centre trial designed to assess the clinical effects of the commercially available Axium® Neurostimulator System in the management of chronic intractable pain. Subjects that are routinely scheduled to receive DRG stimulation will be asked to participate in this trial. They will be screened based upon the inclusion and exclusion criterion, consented with an REC approved Patient Informed Consent Form, and enrolled into the trial. Subjects will then be assessed for baseline measurements.

Patients that are not willing to participate in the trial or that do not fulfill the inclusion criteria, but are, nevertheless, considered to be suitable for neurostimulation will be treated as such under standard of clinical care at the pain clinic.

Subjects will “trial” the therapy with an external Trial NeuroStimulator (TNS), for a maximum of 30 days (Phase 1) depending on standard hospital practice. If subjects obtain sufficient pain relief either overall or in their primary area of pain being treated, they will be eligible to proceed with the second phase of the therapy. If the eligible subjects agree to move forward into Phase 2, they will receive the fully Implantable NeuroStimulator (INS). Subjects will be seen for follow-up at 1 week, 4 weeks, 3 months, 6 months, 12 months and 24 months following implantation (Figure 1). The site can contact the subjects by phone for a follow-up at 8 weeks, 9 months and 18 months (optional).

**Figure 1.** Basic design and follow-up schedule for subjects enrolled into the PREDICT trial. Subjects consented and enrolled will undergo a two-phase process for advancement through the trial. Subjects that do not obtain at sufficient pain relief during Phase 1 will be considered screen failures. A detailed follow-up scheduled can be found in Appendix A.

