### Protocol Phase 1 – Temporary Trial Neurostimulation

Following consent and entry into the prospective trial, baseline assessments will be taken. Subjects will then have the quadrapolar leads epidurally placed using a percutaneous approach and steered towards the appropriate intraspinal location (see *Physician Implant Manual* for detailed information regarding the procedure).

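### The Figure 1 legend calls subjects without enough Phase 1 relief screen failures, although by the protocol's own sequence they are enrolled, have baseline data and have had epidural leads placed

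*Protocol*

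**What the plan says.** The Figure 1 legend in section 3 contains two consecutive sentences about the same people. The first reads: "Subjects consented and enrolled will undergo a two-phase process for advancement through the trial". The second reads: "Subjects that do not obtain at sufficient pain relief during Phase 1 will be considered screen failures".

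The body of section 3 gives the order of entry. Candidates are "screened based upon the inclusion and exclusion criterion, consented with an REC approved Patient Informed Consent Form, and enrolled into the trial", and baseline measurement follows. Section 1.3 describes the therapy as one that "consists of a two-phase treatment process: 1) a temporary trial phase and 2) a permanent implant phase", so Phase 1 is part of the treatment. Section 5.1 describes it the same way.

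The primary objective in section 2 includes the percentage of subjects whose VAS pain falls by half or more. It does not say of which subjects. The Summary and section 3 start the 24-month follow-up at implant, which only subjects with a successful trial phase receive. Section 1.4 gives the aim as long-term data on how the system performs in patients already listed for DRG stimulation in routine practice.

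**The concern.** A screen failure is ordinarily someone who was assessed for entry and did not get in. Such a person is normally left out of the enrolled count, the treated count and any efficacy denominator. Here the term is given to people who did get in and who underwent an invasive procedure.

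Two things are at stake. The first is the account of subjects: people with leads placed could drop out of the enrolled and treated totals. It also becomes unclear whether they count towards the cap of 125 in the Summary, and the no-replacement rule in section 7.5 speaks only of withdrawn subjects. The second is the meaning of the responder percentage. If Phase 1 failures are set aside, it answers how well the system works in those who passed a trial of it. The aim in section 1.4 covers everyone scheduled for the therapy, including those for whom the trial phase fails.

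**Working it through.** **Step 1: what screening means in this protocol.** Section 7.3 has subjects screened against the inclusion and exclusion criteria, and says "only subjects meeting all Inclusion criteria and none of the Exclusion criteria will be enrolled". Section 3 uses the word in the same way. It adds that patients who do not fulfil the inclusion criteria are treated outside the trial under standard care. That is the group the term fits.

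**Step 2: does any criterion concern trial response?** Section 4.2 lists 7 inclusion criteria and section 4.3 lists 11 exclusion criteria. None mentions the response to trial stimulation. A subject without enough Phase 1 relief has therefore failed no screening criterion.

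**Step 3: what has happened by the time relief is judged?**
- Section 7.3, on baseline: "Following subject screening and acquisition of Informed Consent, subjects will undergo a baseline assessment to collect clinical data prior to lead implantation and stimulation".
- Section 3, Phase 1: "Following consent and entry into the prospective trial, baseline assessments will be taken. Subjects will then have the quadrapolar leads epidurally placed".
- Section 7.3, end of trial phase: relief is assessed either in theatre during the trial stimulator procedure or after an extended trial of up to 30 days. On either route the leads are already in.

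The order is eligibility check, consent and enrolment, then baseline, lead placement and judgement of relief. The legend attaches a label from the first step to an outcome of the last.

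**Step 4: effect on the responder percentage.** The protocol states no figure to reproduce, so only the form of the effect can be derived. Let s be the share of trialled subjects who pass Phase 1 and r the share of implanted subjects who are responders. Assume that every passer accepts the implant and that Phase 1 failures count as non-responders.
- Implanted-only share = r
- Share among all trialled = r × s
- Gap = r − r × s = r(1 − s)

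The documents give neither s nor r for this device. The values below are assumptions that show how the formula behaves. Gaps are in percentage points.

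| Assumed s | r = 50% | r = 70% |
|---|---|---|
| 98% | 0.50 × 0.02 = 1.0 | 0.70 × 0.02 = 1.4 |
| 90% | 0.50 × 0.10 = 5.0 | 0.70 × 0.10 = 7.0 |
| 75% | 0.50 × 0.25 = 12.5 | 0.70 × 0.25 = 17.5 |
| 65% | 0.50 × 0.35 = 17.5 | 0.70 × 0.35 = 24.5 |

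In counts, with 125 trialled and an assumed 20% failing Phase 1, 100 are implanted. At r = 50% there are 50 responders: 50/100 = 50% of those implanted, 50/125 = 40% of those trialled. The gap goes to zero as s approaches 100%.

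**The case against.** The strongest reply is that this is one loose term in a figure legend. Trial stimulation can be thought of as a screening trial, the protocol never defines a screen failure, and no visible sentence drops these subjects from any count. Analysis sets, responder denominators and the handling of non-responders usually belong in a SAP, and sections 9.1 and 9.2 are redacted. Much of this stands. A reader might infer that the protocol excludes Phase 1 failures from the primary analysis, and the documents do not support that. What does not stand is the appeal to loose usage: this protocol uses screening only for the check before enrolment, and a SAP would not correct a classification that the protocol itself states.

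A second reply is that the label does not cause the conditioning. Follow-up that starts at implant restricts long-term VAS data to implanted subjects whatever the others are called, and the protocol says so openly. This is right. The label adds to the problem because it gives a reason not to count Phase 1 failures as non-responders, which would otherwise restore the full denominator.

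Third, a reader might infer that safety events in Phase 1 go unreported. The text points the other way: section 8.3 has reportable events documented for the whole of the trial, and section 8.4 has reported events followed up. The safety interest is in the denominator only.

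Fourth, section 1.2 says of existing spinal cord stimulation: "The treatment has been found to be successful in approximately 50% of patients that have a successful temporary stimulation trial period". A reader might infer a planned comparison with that figure, or take it as the responder rate here. Neither is supported. It is background on another form of stimulation, success there is not defined as this trial's VAS criterion, and no visible text plans a comparison.

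**Conclusion.** The contradiction is established from the visible text and depends on neither the redacted sections nor an unseen SAP. The legend classes as screen failures subjects who passed screening, were enrolled and began treatment.

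The consequence is conditional. Only if the label is applied literally do treated subjects leave the enrolled account and does the responder share become tied to a successful trial phase without saying so. Whether that will happen cannot be seen, so the biased denominator remains a risk. Its size is r(1 − s), given full acceptance of the implant and Phase 1 failures counted as non-responders. Under the assumed rates shown it runs from about 1 to 24.5 points, and the documents do not say where in that range, or outside it, this trial would fall. The implanted-only share is a legitimate quantity if it is labelled as such. The point should be fixed because the wording is wrong on the protocol's own terms, bears on a primary measure and is cheap to correct.

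**What to change.** - Reserve the term screen failure for subjects who do not meet sections 4.2 and 4.3 and so are not enrolled.
- In the Figure 1 legend, call the others Phase 1 (trial stimulation) failures, and state that they stay in the enrolled, treated and safety counts.
- Report the Phase 1 pass rate.
- Give the responder share among all subjects who had the trial stimulator procedure, with Phase 1 failures as non-responders, beside the implanted-only share. Label each with its denominator, and show subjects who pass but decline the implant separately.

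The clinical gate to implant is unchanged. The cost is one reworded sentence, one statement of the two denominators and one more table, with no extra patients, visits or procedures. The downside for the sponsor is a second, less favourable figure in the report.
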